Therapeutic PE and IVIg are rapid but short-acting immunomodulating treatments. As such, they are typically used in patients with acute severe gMG when a rapid response is crucial, and are the mainstay of management of myasthenic crisis. As their effect is short-lived (4–12 weeks), maintenance immunotherapy is usually needed. They may be used as chronic, maintenance therapy in patients with refractory gMG (see Section 4.5.3 for definition) or in patients for whom immunosuppressive agents are relatively contraindicated, such as the pediatric population.

Thymectomy is indicated for patients with thymoma if resection is feasible and in many other AChR antibody–positive patients with non-thymomatous gMG who are 18–65 years old. In patients with a non-neoplastic thymus, thymectomy for the improvement of gMG has been performed for several decades, and is supported by extensive evidence on the pathogenetic role of the thymus in AChR + gMG and by a large number of studies showing a higher remission rate after thymectomy (Skeie et

al. 2010; Wolfe et al. 2016; Gronseth et al. 2020). The role and timing of thymectomy is still not well established or standardized in children. It is usually considered as a therapeutic option in AChR+gMG when the response to pyridostigmine and ISTs is incomplete or to avoid the long-term side effects of ISTs, especially corticosteroids. Thymectomy does not have an effect in MuSK gMG and has not been systematically examined in patients with gMG who have no detectable antibodies. Thymectomy does not cure gMG, and the long-term effect on antibody concentrations, T-cell subsets, and immune responses is very modest.

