## 3.1.5 Unscheduled Visits and Rescue Therapy

Unscheduled visits can be performed at the discretion of the treating neurologist.

If a suspected gMG exacerbation occurs during the study, the participant should return to the study site and undergo the following evaluations before or immediately after any administration of the rescue therapy: MG-ADL, QMG, Myasthenia Gravis Composite

(MGC), and Myasthenia Gravis Quality of Life 15 Scale (revised) (MG-QOL 15r). Additional assessments, such as hematology, chemistry, and urinalysis, will be performed if an infection or a metabolic disturbance is suspected to be contributing to the clinical presentation necessitating the unscheduled visit.

MG exacerbation requiring rescue therapy is defined as one of the following:

- MG crisis (Sanders et al. 2016)
- Substantial symptomatic worsening that requires immediate therapy
- Health in jeopardy if rescue therapy is not given, as determined by the treating physician.

Rescue therapy includes IVIg and PE with or without high -dose corticosteroids as outlined in Section 4.3.3. The choice of rescue therapy will be determined by the investigator on the basis of his or her overall clinical assessment.

Study drug administration will be continued as scheduled, concurrently with rescue therapy, unless the investigator considers it necessary to interrupt or discontinue study treatment (see Section 5.1.4). Patients who receive PE as rescue therapy will receive loading doses of study drug as soon as possible post -PE. Site staff should consult the Medical Monitor as to how to schedule dosing in such circumstances.

Patients who receive rescue therapy during the DB period may receive OLE satralizumab after completion of the DB period.

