### 4.1.1 Inclusion Criteria

Patients must meet the inclusion criteria below to be eligible for study entry.

- Signed Informed Consent Form
- Age  $\geq$  12 years (or  $\geq$  18 years in France) at time of signing Informed Consent Form
- For adolescent patients: Informed Consent Form for study participation signed by the parents or a legal guardian, and patient assent obtained, as per local requirements
- Ability to comply with the study protocol
- Confirmed diagnosis of gMG meeting the following criteria:
  - Documented history of myasthenic weakness
  - MG severity of MGFA Class II, III, or IV at screening
  - The confirmation of the diagnosis has to be documented and supported by positive serologic test for one of the three antibody types: anti--AChR, anti--MuSK or anti--LRP4 at screening (antibody status must be confirmed by

٠

<sup>2 Patients with MG Class IV at participating sites in France are excluded from the study.

the central laboratory for all antibody types). For sites in Germany and the Netherlands, confirmation of the diagnosis has to be documented and supported by pre-existing positive serologic test results for one of the three antibody types (anti-AChR, anti-MuSK, or anti-LRP4), which must have been ordered by a health care professional (HCP) for the patient as part of the patient's historical SOC.

- A total MG-ADL score of ≥ 5 points at screening with more than 50% of this score attributed to non-ocular items
- Ongoing gMG treatment at a stable dose and not exceeding the maximum allowed doses specified in Section 4.3.2.3, as defined below:
  - For patients receiving azathioprine, treatment for at least 6 months and a dose that has been stable for at least 2 months prior to screening
  - For patients receiving other ISTs (i.e., mycophenolate mofetil, cyclosporine, tacrolimus), treatment for at least 3 months and a dose that has been stable for at least 4 weeks prior to screening
  - For patients receiving OCS, treatment for at least 3 months and a dose that has been stable for at least 4 weeks prior to screening
  - For patients receiving an AChEI, treatment with a dose that has been stable for at least 2 weeks prior to screening
- No contraindication to at least one of the rescue treatments: IVIg, PE, or high-dose corticosteroids

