- Evidence of latent or active tuberculosis (TB), excluding patients receiving chemoprophylaxis for latent TB infection

A TB test (tuberculin skin test and/or an interferon-gamma release assay [e.g., QuantiFERON®-TB Gold In-Tube assay, T-SPOT TB assay]) should be conducted according to local guidance. If a patient is positive for latent TB, then the patient must be treated with appropriate anti-mycobacterial therapy for at least 4 weeks prior to initiating study treatment administration. Refer to Appendix 5 for details on TB screening and treatment.

- Receipt of live or live attenuated vaccine within 6 weeks prior to baseline
- History of blood donation (one unit or more), plasma donation or platelet donation within 90 days prior to screening and Day 1
- History of malignancy within the last 5 years, including solid tumors, hematologic malignancies and in situ carcinoma (except basal cell and squamous cell carcinomas of the skin, or in situ carcinoma of the cervix uteri that have been completely excised and cured)
- History of severe allergic reaction to a biologic agent (e.g., shock, anaphylactic reactions)
- Active suicidal ideation within 6 months prior to screening or history of suicide attempt within 3 years prior to screening
- Any serious medical condition or abnormality in clinical laboratory tests that, in the investigator's judgment, precludes the patient's safe participation in and completion of the study

 Pregnant or breastfeeding, or intending to become pregnant during the study or within 3 months after the final dose of satralizumab

Female patients of childbearing potential must have a negative serum pregnancy test result at screening prior to initiation of study drug.

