# 4.3.3 Rescue Medication

Patients may receive rescue therapy in case of MG clinical deterioration/exacerbation on any study day. Exacerbation of MG is defined in Section 3.1.4.

Rescue therapy includes IVIg (2 g/kg administered over a 2- to 5- day period), or PE with or without high-dose corticosteroids (500–1000 mg/day IV methylprednisolone or equivalent for 2–5 days). High-dose corticosteroid therapy should always be administered in combination with IVIg or PE.

The choice of rescue therapy will be determined by the investigator on the basis of his or her overall clinical assessment.

Study drug administration will be continued as scheduled, concurrently with rescue therapy, unless the investigator considers it necessary to discontinue study treatment.

Patients who receive PE as rescue therapy will receive re-loading doses of study drug as soon as possible post-PE (see Section 4.3.2.2, Table 7).

All efforts should be made by the investigator to keep patients in the study during the DB period and continue study drug administration even after experiencing a MG exacerbation requiring rescue therapy.

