# 4.4.1 Permitted Therapy

Patients are permitted to use the following therapies during the study:

- Oral contraceptives (see Section 4.1.1)
- Hormone-replacement therapy
- Background treatment with any of the drugs listed in Section 4.3.2.3

The dose must not exceed the dose defined in Section 4.3.2.3. In the DB period, a dose decrease of baseline treatments is permitted only for safety reasons. Dose increase or change of background treatment is strongly discouraged.

 Rescue therapy in case of acute MG exacerbation defined as IVIg and/or PE administered with or without pulse IV corticosteroids (see Section 4.3.3)

The choice of rescue therapy will be determined by the investigator on the basis of his or her overall clinical assessment.

Study drug administration will be continued as scheduled, concurrently with rescue therapy, unless the investigator considers it necessary to discontinue study treatment.

- Treatment with topical (e.g., ophthalmic, nasal, otic, cutaneous) corticosteroids for adverse events (i.e., indications other than background MG therapy), provided that the duration of treatment is kept as short as possible.
- Pain medications (including topical agents, antiepileptic drugs [e.g., pregabalin, gabapentin, carbamazepine], antidepressants [tricyclic antidepressants and serotonin norepinephrine reuptake inhibitors, e.g., duloxetine], and non-opioid analgesics [e.g., acetaminophen, non-steroidal anti-inflammatory drugs]).

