1.2.1 Treatment Assignment

The study uses an interactive voice/web-based response system (IxRS) to randomize participants to two treatment arms and ensure blinding of both treating physician and the participant and the Sponsor. The IxRS implements a block randomization scheme with a block size specified in the Biostatistics Randomization Specification Document. Treatment assignments are stratified and hence balanced across the following baseline factors:

- Region: North America versus Europe versus Rest of World
- Baseline SOC treatment: AChEI monotherapy and/or an OCS versus a steroid-sparing IST monotherapy or a combination of steroid-sparing IST with other treatments (an AChEI and/or an OCS)
- Auto-antibody type: AChR-antibody positive versus AChR-antibody negative (includes MuSK or LRP4 antibody-positive)
- If a stratification factor level has a very low sample size compared to other levels, the Sponsor may group the levels together for the statistical analysis. Such a grouping would be determined before the data are unblinded.

1.2.2 Data Monitoring

An iDMC will be used during the DB period and until the database lock for the primary analysis. The iDMC will perform periodic (approximately every 3 months scheduled in agreement with the iDMC) unblinded safety reviews and make recommendations on trial continuation or modification. The iDMC will be involved in the interim PK analysis as detailed in the iDMC charter. All summaries and analyses will be prepared by the iDCC and presented by treatment group for the iDMC's review. Members of the iDMC and iDCC will be external to the Sponsor and the study team and will follow the iDMC charter that outlines their roles and responsibilities. The Sponsor will remain blinded. Interactions between the iDMC and Sponsor will be carried out as specified in the iDMC Charter.

1.2.3 Global Protocol Version 5

In July 2023, the Global Protocol was amended to Version 5 resulting in a sample size reduction. Given the number of participants already recruited, screening of new participants was stopped for adult participants. Due to recruitment difficulties for adolescents related to placebo use in the double-blind period, adolescents will continue to be recruited and will enroll directly into the OLE period, once the protocol amendment is approved in their countries. Adolescents who are enrolled in the study after the last adult was randomized will not contribute to the primary analysis.

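### The protocol contradicts itself on corticosteroid rescue: Section 4.1.1 admits a patient for whom high-dose corticosteroid is the only usable rescue treatment, but Sections 4.3.3 and 4.4.1 give that patient no regimen

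*Protocol*

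**What the plan says.** The eligibility rule is in Protocol Section 4.1.1: "No contraindication to at least one of the rescue treatments: IVIg, PE, or high-dose corticosteroids". The list is disjunctive, so any one of the three is enough. Section 3.4.7.4, which explains how rescue is handled in the responder definition, names the same three treatments as the ones available. Appendix 15 designates IV methylprednisolone as a rescue medication.

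The sections that govern how rescue is given read differently:

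- Section 4.3.3 describes IVIg, or PE with or without high-dose corticosteroid, and adds: "High-dose corticosteroid therapy should always be administered in combination with IVIg or PE".
- Section 4.4.1 permits "Rescue therapy in case of acute MG exacerbation defined as IVIg and/or PE administered with or without pulse IV corticosteroids".
- Section 3.1.5 has the same structure and defers to 4.3.3: "Rescue therapy includes IVIg and PE with or without high -dose corticosteroids as outlined in Section 4.3.3".

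No exclusion in Section 4.1.2 names a contraindication to IVIg or PE. The nearest is in 4.1.2.3, which excludes a serious medical condition or laboratory abnormality that "in the investigator's judgment, precludes the patient's safe participation in and completion of the study".

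**The concern.** The 4.1.1 bullet is the only eligibility criterion that checks whether a patient could receive rescue treatment. If it is there to make sure that each patient can receive the rescue the protocol describes, its wording does not do so. A patient for whom both IVIg and PE are contraindicated passes on corticosteroid alone, and the rescue sections then offer that patient nothing.

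The consequence is a safety matter. Under Section 3.1.5, rescue is for a myasthenic crisis, for worsening that needs immediate treatment, or for a patient whose health is in jeopardy without it. Section 1.3 says that PE and IVIg "are the mainstay of management of myasthenic crisis". Section 6.1 assumes rescue in about 10% of the satralizumab group and 20% of the placebo group. Those rates are for the double-blind AChR+ population and do not carry over to adolescents in the open-label extension (OLE), but they show that rescue is an expected event in this trial. An investigator treating such a patient in an emergency would find instructions that do not fit.

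**Working it through.** No figure in the plan is at issue, so the check is logical. Each of IVIg, PE and high-dose corticosteroid is either usable or contraindicated for a given patient, which gives 2 × 2 × 2 = 8 combinations. The two rules are:

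- Eligible under 4.1.1: at least one of the three is usable.
- Regimen described under 4.3.3 and 4.4.1: IVIg or PE is usable, with corticosteroid only as an addition.

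| IVIg | PE | Corticosteroid | Eligible (4.1.1) | Regimen (4.3.3, 4.4.1) |
|---|---|---|---|---|
| usable | usable | usable | yes | yes |
| usable | usable | contraindicated | yes | yes |
| usable | contraindicated | usable | yes | yes |
| usable | contraindicated | contraindicated | yes | yes |
| contraindicated | usable | usable | yes | yes |
| contraindicated | usable | contraindicated | yes | yes |
| contraindicated | contraindicated | usable | **yes** | **no** |
| contraindicated | contraindicated | contraindicated | no | no |

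Eligible: 8 − 1 = 7. With a described regimen: (4 − 1) × 2 = 6. Eligible without a regimen: 7 − 6 = 1, the row in bold. These are counts of logical cases, not of patients. They say nothing about how often the case occurs.

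Next, does other text close the gap?

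- Section 3.4.7.4 lists corticosteroid as available but gives no corticosteroid-alone regimen. Appendix 15 is a regulatory designation and gives none either.
- Section 4.1.2.3 leaves exclusion to the investigator's judgment and does not mention rescue.
- Section 4.3.3 leaves the choice of rescue to the investigator, directly after describing regimens that all include IVIg or PE.

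None of these closes it.

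Who is still affected? SAP Section 1.2.3 says that "screening of new participants was stopped for adult participants", while "adolescents will continue to be recruited and will enroll directly into the OLE period". A change to eligibility therefore reaches only those adolescents. A change to the rescue sections also reaches patients already enrolled, because 4.3.3 allows rescue on any study day.

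The two possible corrections can be run through the same table. Restricting 4.1.1 to IVIg or PE makes 6 cases eligible, all 6 with a regimen. Adding a corticosteroid-only exception to 4.3.3 and 4.4.1 leaves 7 eligible, all 7 with a regimen. Either removes the gap.

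**The case against.** The strongest reply is that 4.1.1 is not an isolated slip. Section 3.4.7.4 has the same three-item list, and Appendix 15 treats IV methylprednisolone as a rescue medication authorized for myasthenia gravis in the European Economic Area. Section 4.3.3 gives a full corticosteroid dose, says *should* rather than *must*, and leaves the choice to clinical assessment. Section 3.1.5 says that rescue *includes* IVIg and PE, which need not be exhaustive. On this view the sponsor may accept corticosteroid alone when nothing else is possible, and the rescue sections are merely worded too tightly.

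Most of this stands as a limit on the point. It leaves the sponsor's intent open, so 4.1.1 cannot be assumed to be the text in error. It does not remove the contradiction: 4.3.3 says *always*, and no section describes corticosteroid given alone.

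A reader might infer that treatment would be withheld from such a patient. The documents do not support that, because 4.3.3 leaves room for judgment and Section 4.4.3 does not prohibit high-dose corticosteroid. Nor do they say that departing from the combination advice would be a protocol deviation.

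The affected group may also be empty. Section 1.3 mentions IVIg and PE as maintenance options where immunosuppressants are relatively contraindicated, with pediatric patients as an example, which suggests that both are established in the group still being recruited.

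**Conclusion.** The contradiction is real and minor. Two sections treat high-dose corticosteroid as a rescue treatment in its own right, and two allow it only alongside IVIg or PE. One type of patient, contraindicated to both IVIg and PE but not to corticosteroid, is eligible without a rescue regimen under 4.3.3 or 4.4.1, and only a discretionary exclusion might catch this.

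The size cannot be computed. The documents give no frequency for this combination and do not show that such a patient was enrolled; the number is probably small. The view that 4.1.1 is meant to guarantee access to rescue is an inference, since no section states its purpose. The inconsistency between the sections does not depend on it.

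A reader might infer that efficacy results are at risk. They are not. The responder rule turns on whether rescue was received, and 3.4.7.4 counts high-dose IV corticosteroid as rescue for that purpose. Adolescents now entering the OLE do not contribute to the primary analysis. Sample size, power and alpha do not change.

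**What to change.** Decide which rule is intended and align the sections at the next amendment.

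- **If IVIg or PE is the required backbone:** change the 4.1.1 bullet to *No contraindication to at least one of IVIg or PE*, and bring 3.4.7.4 into line. This agrees with 4.3.3, 4.4.1 and the statement in 1.3 on crisis management. The cost is that a rare adolescent becomes ineligible for a cohort that was opened because recruitment was difficult. It does nothing for any such patient already enrolled.
- **If corticosteroid alone is acceptable when both are contraindicated:** keep 4.1.1 and state that exception in 4.3.3 and 4.4.1. Section 3.1.5 already defers to 4.3.3. This agrees with 3.4.7.4 and Appendix 15, covers enrolled patients and excludes nobody.

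Either is two short wording edits. The second costs less, but it should be chosen only if the sponsor considers corticosteroid alone clinically adequate for these patients. Neither needs a change to the SAP.

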## 4.1.2 Exclusion Criteria

Patients who meet any of the exclusion criteria listed below will be excluded from study entry.

#### 4.1.2.1 Exclusion Criteria Related to Myasthenia Gravis:

Patients who meet any of the following MG-related criteria will be excluded from the study:

- History of thymic cysts, thymoma, thymic carcinoma or other neoplasm of the thymus as defined by the 2015 WHO classification of tumors of the thymus (Marx et al. 2015) unless deemed cured by adequate treatment with no evidence of recurrence for ≥ 5 years before screening.
- History of thymectomy within 6 months prior to screening
- Ocular MG (MGFA Class I)
- In France, MGFA Class IV MG at screening
- Myasthenic crisis within the last 3 months prior to screening (MGFA Class V)
- Known disease other than gMG that would interfere with the course and conduct of the study (such as severe RA or symptomatic [overt] hyperthyroidism or hypothyroidism)

# 4.1.2.2 Exclusion Criteria Related to Previous or Concomitant Therapy:

Patients who meet any of the following criteria related to previous or concomitant therapies will be excluded from the study:

- Use of IVIg or subcutaneous immunoglobulin (SCIg) within 6 weeks prior to randomization/Day 1
- Use of PE within 8 weeks prior to randomization/Day 1
- Treatment with IL-6 inhibitory therapy (e.g., tocilizumab) at any time
- Treatment with total body irradiation, or bone marrow transplantation at any time

- Treatment with B and/or T cell-depleting agents (except anti-CD20 agents) including, but not limited to, inebilizumab and alemtuzumab at any time
- Treatment with anti-CD20 within 6 months prior to screening, unless CD19 counts are within normal range, as assessed by the central laboratory at screening
- Treatment with C5 complement inhibitors (e.g., eculizumab or ravulizumab) within
   6 months prior to screening
- Treatment with neonatal Fc receptor antagonists within 6 months prior to screening
- Treatment with anti–B-lymphocyte stimulator monoclonal antibody (e.g., belimumab) at any time
- Treatment with cyclophosphamide IV within 6 months prior to screening
- Treatment with oral cyclophosphamide at any time
- Treatment with methotrexate within 8 weeks prior to screening
- Treatment with any investigational agent within 24 weeks prior to screening or 5 drug-elimination half-lives of the investigational drug (whichever is longer)
- Use of more than one IST (azathioprine, mycophenolate mofetil, cyclosporine A, tacrolimus) as background therapy except for the combination of an OCS with another permitted IST drug

# 4.1.2.3 General Safety Exclusion Criteria:

Patients who meet any of the following safety-related criteria will be excluded from the study:

- Any surgical procedure (except for non-ophthalmic minor surgeries\*) within 4 weeks prior to screening
- Planned surgical procedure (except for non-ophthalmic minor surgeries\*) during the study
  - \* Note: A minor surgical procedure is considered a procedure that requires only local anesthesia or conscious sedation (does not require general, neuraxial or regional anesthesia) and is done on an ambulatory/outpatient basis (e.g., toenail surgery, mole surgical excision, wisdom tooth extraction).

Note: All ophthalmic surgical procedures, major or minor, including strabismus surgeries, are prohibited within 4 weeks prior to screening and should not be planned during the study.

- Evidence of progressive multifocal leukoencephalopathy
- Evidence of serious uncontrolled concomitant diseases that may preclude patient participation, such as other nervous system disease, cardiovascular disease, hematologic/hematopoiesis disease, respiratory disease, muscular disease, endocrine disease, including thyroid disease, renal/urologic disease, digestive system disease
- Congenital or acquired immunodeficiency, including HIV infection

- Active or recurrent bacterial, viral, fungal, mycobacterial infection, or other infection (excluding fungal infection of nail beds or dental caries) at baseline
- Infection requiring hospitalization or treatment with IV anti-infective agents within 4 weeks prior to baseline visit or oral anti-infective agents within 2 weeks prior to baseline visit
- Positive screening tests for hepatitis B, defined as either of the following:
  - o Positive hepatitis B surface antigen [HBsAg]
  - Positive total hepatitis B core antibody [total HBcAb] confirmed by a positive viral DNA PCR
- Positive screening test for hepatitis C (defined as positive hepatitis C virus [HCV] antibody and detectable HCV RNA)

Participants with positive HCV antibody and undetectable HCV RNA 12 weeks after HCV treatment completion are eligible to participate in the study.

- History of drug or alcohol abuse within 1 year prior to baseline
- History of diverticulitis or concurrent severe GI disorders (such as symptomatic diverticulosis) that, in the investigator's opinion, may lead to increased risk of complications such as GI perforation
- Evidence of latent or active tuberculosis (TB), excluding patients receiving chemoprophylaxis for latent TB infection

A TB test (tuberculin skin test and/or an interferon-gamma release assay [e.g., QuantiFERON®-TB Gold In-Tube assay, T-SPOT TB assay]) should be conducted according to local guidance. If a patient is positive for latent TB, then the patient must be treated with appropriate anti-mycobacterial therapy for at least 4 weeks prior to initiating study treatment administration. Refer to Appendix 5 for details on TB screening and treatment.

- Receipt of live or live attenuated vaccine within 6 weeks prior to baseline
- History of blood donation (one unit or more), plasma donation or platelet donation within 90 days prior to screening and Day 1
- History of malignancy within the last 5 years, including solid tumors, hematologic malignancies and in situ carcinoma (except basal cell and squamous cell carcinomas of the skin, or in situ carcinoma of the cervix uteri that have been completely excised and cured)
- History of severe allergic reaction to a biologic agent (e.g., shock, anaphylactic reactions)
- Active suicidal ideation within 6 months prior to screening or history of suicide attempt within 3 years prior to screening
- Any serious medical condition or abnormality in clinical laboratory tests that, in the investigator's judgment, precludes the patient's safe participation in and completion of the study

 Pregnant or breastfeeding, or intending to become pregnant during the study or within 3 months after the final dose of satralizumab

Female patients of childbearing potential must have a negative serum pregnancy test result at screening prior to initiation of study drug.

